Study staff will ensure that any adverse study medication events which occur will be documented and immediately reported to the principal investigator. They should also be reported to the reviewing Ethics Committee and institution as soon as possible, no later than fifteen working days after the investigator learns of the event. An evaluation of the adverse events will be conducted by the investigator. Following this, if it is determined that the adverse effect presents an unreasonable risk to participants, the trial will be terminated as soon as possible. Termination shall occur no later than five working days after the investigator makes the determination, and no later than fifteen working days after the investigator first receives notice of the adverse event.

Serious Adverse Events (SAEs)

Any adverse event considered to be serious in nature which occurs at any time point from signing of Informed Consent Form until either the patient is terminated from the study, or 7 days post-completion, should be recorded as follows:

- All SAEs should be reported immediately to the principal investigator no later than 24 hours after becoming aware of the event.
- This will be followed promptly by detailed, written reports.

• The investigator should comply with the applicable regulatory requirement(s) related to the reporting of serious unexpected adverse study medication reactions to the regulatory authority (MedSafe NZ) and the Ethics Committee.

 All other SAEs not related to the study medication will be reported to the Ethics Committee as directed.

Ethics Committee

Approval

The investigator is responsible for obtaining Ethics Committee and Governance approval to conduct this study

Prior to Initiation of the Study

Written approval by the Ethics Committee and Governance must be obtained prior to beginning the study. Discussions may be had with prospective participants regarding the study, however written Patient Informed Consent must not be obtained. Until all approvals are granted, study procedures must also not be performed on prospective study participants.

Progress Reports

Progress reports on the trial will be submitted by the investigator at the request of the Ethics Committee.

Final Reports

Upon completion of the investigation, each investigator will submit an Ethics Close-Out Report on his/her part of the investigation within three months of completion of the investigation. This will be submitted to the Ethics Committee.

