- Quality of life/functional outcome comparisons using the KOOS Jr score, Oxford Knee Score (OKS), numerical rating scales (NRS) of gait/walking ability and sleep.
- Post-operative recovery comparisons using the Quality of Recovery 15 (QoR-15) survey and comparing average length of stay (LoS) for each study group

Questions to be answered:

- Is IORA of Diclofenac or systemic Diclofenac more effective in managing post-operative pain (as judged by VAS-P scores).
- 2. Will IORA of combined Diclofenac or systemic Diclofenac result in a more significant reduction in additional systemic opioid use for post-operative analgesia (as judged by MME).
- 3. Will IORA of Diclofenac or systemic Diclofenac provide better clinical improvement in knee health recovery and outcomes (as judged by KOOS Jr, OKS, NRS gait/walking ability and sleep, QoR-15, LoS).

Study Design

A prospective, double blinded RCT, with a single site cohort.

Patients and Methods

Patients who will be undergoing primary TKA for osteoarthritis will be eligible for this prospective study and randomised into two groups with 23 participants in each, one group receiving IORA Diclofenac (intervention group), and one group receiving IV Diclofenac (control group).

Power Calculation

There is a paucity of data evaluating the efficacy of IORA in pain management following TKA because it is a novel technique, although postoperative pain management is a thoroughly investigated area. Sample size was calculated based on previously published data investigating the efficacy of perioperative Celecoxib (a NSAID) on postoperative pain (VAS pain) after TKA [32]. This study showed statistically significant improvements in VAS pain scores for the intervention group (Celecoxib and PCA Morphine) at 48 hours and 72 hours after TKA, compared to the control group (PCA Morphine only). Mean VAS pain scores (in mm) in the intervention group were 21.3 ± 16.8 at 48 hours, and 17.8 ± 16.6 at 72 hours. Whereas VAS pain scores in the control group were 34.3 ± 15.0 at 48 hours, and 31.7 ± 20.1 at 72 hours.

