A record of the patient's date of birth, age, gender, weight, height, BMI, and medical history will be obtained pre-operatively at time of consent.

Patient Catastrophising Scale (PCS)

A self-reported measure which assesses catastrophic thinking in the context of actual or anticipated pain. Pain catastrophising is associated with poor pain treatment response in patients with chronic pain [35].

Pain Disability Index (PDI)

A widely used tool for determining pain-related disability. It measures the degree to which chronic pain disrupts different aspects of life.

KOOS, Jr Survey

The Knee Injury and Osteoarthritis Outcomes Score for Joint Replacement survey provides a single score that represents "knee health" as it combines pain, symptoms, and functional limitations [31]. It is a patient reported outcome measurement instrument developed to assess the patient's opinion about their knee and associated problems.

Oxford Knee Score (OKS)

A patient-completed 12-item questionnaire, designed specifically for patients undergoing total knee replacement. Relates to an individual's level of function, activities of daily living, and how they have been affected by pain. Each of the 12 items has 5 scoring categories. It is short, practical, reliable, valid and sensitive to clinically important changes over time.

Visual Analogue Scale Pain (VAS-P)

A graphic VAS will be used as a measurement instrument for patients to indicate their level of pain on a scale from 'No Pain' to 'Worst Pain Possible'. VAS is a continuous spectrum to represent pain.

Morphine Milligram Equivalent (MME)

MME is the amount of morphine in milligrams equivalent to the strength of the opioid dose prescribed. This measurement will allow for a standardised comparison of opioid use between study groups.

Patient Satisfaction

Numerical rating scale (NRS; 0-10) for grading a patient's satisfaction with their knee replacement, from 'completely dissatisfied' to 'completely satisfied'.

Gait/Walking Ability and Sleep

NRS (0-10) for grading how pain has interfered with a patient's walking ability and sleep over the past 24 hours, from 'does not interfere' to 'completely interferes'.

Average Length of Stay (LoS)

Each patient's length of stay in hospital will be recorded from day of admission to day of discharge.

Quality of Recovery (QoR-15)

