A patient reported outcome questionnaire to measure the quality of recovery after anaesthesia, which is important in determining early postoperative health status of patients.

Outcomes

Preoperative Outcome Measurements

The following outcome measurements will need to be completed by patients prior to their surgery. Baseline scores will be averaged for each study group:

- PCS A PCS score of ≥ 30 represents clinically relevant catastrophising and will exclude patients from the study.
- PDI
- KOOS, Jr
- OKS
- Preoperative VAS-P score
- Preoperative opioid use (MME) Participants will be required to report any and all opioid
 pain medications (including Tramadol and Codeine) they use as well as the average daily
 amount of opioid medications in milligrams that they take. For example, 20 mg of Sevredol
 daily. This will be converted into a preoperative baseline MME.

Postoperative Outcome Measurements

The primary outcome of this study will be patient pain levels during the early stages of recovery following primary total knee arthroplasty. To monitor this, pain at rest scores will be recorded by the patient using the Visual Analogue Scale (VAS; 0-100 mm from "no pain" to "worst pain possible"). The distance between "no pain" and the patient-made mark is to be measured to the nearest 1 mm.

Post-operatively, once the patient has arrived at the recovery unit, pain scores are to be recorded at the following time points: 1 hour, 2 hours, 3 hours, 4 hours, 5 hours, 12 hours, and 24 hours post-op. These numbers will be recorded by a recovery nurse who will be blinded to the treatment group, and by a treating physio the following day. Patients will also record twice daily VAS-P scores at 8am and 5pm from post-op day 1, up to post-op day 7, into a pain diary supplied to them. These twice daily recordings will be used to calculate daily averages of pain scores. All VAS-P scores are to be recorded for 'pain at rest'.

The minimal clinically important difference (MCID) of 20 mm for VAS-P scores will be used to determine the clinical significance of pain relief in the intervention group compared to the control group.

Secondary outcomes which focus on function, pain, satisfaction, and health related quality of life:

• Total Morphine Milligram Equivalent (MME) of additional postoperative opioid medications required for 1 week post-op (from post-op day 0 to post-op day 7).

- Quality of recovery after anaesthesia (as per QoR-15 survey), recorded post-op day 1.

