- NRS for gait/walking ability, sleep. To be recorded for 1 week post-op.
- Participant length of hospital stay, from date of admission to date of discharge.
- NRS for patient satisfaction, recorded at post-op weeks 2 and 6.
- KOOS, JR scores at post-op weeks 2 and 6.
- OKS at post-op week 6.

Indirect measure of pain will be gauged from the total MME dosing for each patient which will be an indicator of postoperative opioid use burden. Patients will be required to record in their pain diaries the amount, in milligrams, of additional opioid medication they are taking per day up to post-op day 7, which will then be converted into daily MME. Patients will also be required to record on a NRS how much pain has interfered with their walking ability and sleep over the previous 24 hours, up to post-op day 7 in their pain diaries.

[figure not shown]
An automated texting service will be used to remind patients to fill out their pain diary.

Length of stay from date of admission to date of discharge will be recorded for all participants on their pain diaries. Average length of stay will be calculated for each study group and compared.

Participants will be followed up in a 2 week post-op clinic where the pain diaries are to be collected. At this clinic, participants will be required to complete a KOOS Jr survey and NRS for patient satisfaction relating to their knee replacement. At the 6-week post-op mark patients will be seen in clinic again and will be required to complete a KOOS Jr survey, patient satisfaction NRS, and OKS. The means of these outcomes will be compared between the study groups at each particular time point.

Participants will be provided patient information leaflets detailing potential adverse effects of Diclofenac. If any adverse effects occur, participants are to report to nursing staff, who will inform the treating doctor/researcher. We predict side effects from a single preoperative dose of Diclofenac are unlikely to arise after discharge i.e., a few days post-op.

Study Timeline

Data Capture and Analysis

Data will be recorded on Case Report Forms (CRFs; includes patient pain diaries). An investigator will complete and sign forms once they are completed by patients. The data will then be entered onto a secure excel spreadsheet by a research assistant. The original paper CRFs are to be stored securely, and archiving to be undertaken in accordance with ICH/GCP guidelines.

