Means, standard deviation, and 95% confidence intervals will be calculated for the participant VAS-P scores at each recorded time interval as the primary objective of the study. A general linear model or generalised linear mixed model, followed by independent two-sample t-test or Wilcoxon non-parametric rank sum test will be used to analyse the data. VAS-P scores will be pooled according to the appropriate study group for comparison between the study arms. An MCID of 20 mm will be used to determine a clinically significant difference in pain management (but not necessarily statistical significance).

For secondary objectives, independent two-sample t-test or Wilcoxon non-parametric rank sum test will be used to compare means of MME, LoS, QoR-15, satisfaction, gait, sleep, OKS, KOOS Jr scores between the intervention group and control group.

The intended statistical test used will be dependent on the distribution of the data collected. This will be determined by appropriate normality and homogeneity testing of the data. If requirements

are not met, a transformation may be applied, which will likely be logarithmic. Adjustments will be made accordingly based on the data obtained.

Baseline characteristics and preoperative survey scores will be compared using a two sample t-test or Wilcoxon non-parametric rank sum test. Gender comparisons between the two study groups will need to be analysed using a two-way analysis of variance (ANOVA) or in the case of non-parametric testing, Kruskal-Wallis test.

Adverse events will be recorded separately and reviewed by investigators for relevance to the procedure/intervention as well as commonalities. Frequency and percent distributions will be presented in tabular form and logistic regression will be used for comparison of the study groups.

The statistical principles of this protocol have been reviewed by a Consultant Statistician who will also oversee statistical analysis.

Selection Criteria for Investigators/Sites

- The investigator(s) participating in this study is(are) qualified Orthopaedic surgeon(s).
- Research assistants and study staff will be under the direction of the Principal investigator.
- Conflicts of interest (including financial assistance from other parties) will be declared by Investigators and research personnel before starting the trial.
- A list entailing any persons, their qualifications, and their roles relating to the trial, must be kept by the investigators.

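### Study question 3 asks about improvement in walking and sleep, but neither 0-10 rating is taken before surgery; two preoperative items and a rewording would put this right

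*Protocol*

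**What the plan says.** Question 3, under Questions to be answered in the Objectives, asks which treatment will "provide better clinical improvement in knee health recovery and outcomes (as judged by KOOS Jr, OKS, NRS gait/walking ability and sleep, QoR-15, LoS"). The secondary objectives just above it use more neutral terms: "Quality of life/functional outcome comparisons using the KOOS Jr score, Oxford Knee Score (OKS), numerical rating scales (NRS) of gait/walking ability and sleep", and "Post-operative recovery comparisons using the Quality of Recovery 15 (QoR-15) survey and comparing average length of stay (LoS) for each study group".

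The two ratings are defined under Evaluations as "NRS (0-10) for grading how pain has interfered with a patient's walking ability and sleep over the past 24 hours". Their timing is given under Postoperative Outcome Measurements: "NRS for gait/walking ability, sleep. To be recorded for 1 week post-op". QoR-15 is a single early measurement: "Quality of recovery after anaesthesia (as per QoR-15 survey), recorded post-op day 1".

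The preoperative list opens with "The following outcome measurements will need to be completed by patients prior to their surgery" and then names PCS, PDI, KOOS Jr, OKS, VAS-P and opioid use as MME. The Patient Evaluation Schedule agrees: gait and sleep are marked only at 1 week after surgery and QoR-15 only on day 1, while KOOS Jr and OKS have a preoperative mark. In Data Capture and Analysis, a two-sample t-test or a Wilcoxon rank sum test "will be used to compare means of MME, LoS, QoR-15, satisfaction, gait, sleep, OKS, KOOS Jr scores" between the arms.

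**The concern.** Improvement ordinarily means change from an earlier state. For the walking and sleep ratings that earlier state is never recorded, although the items could be asked before surgery: every participant has knee osteoarthritis, and the items ask how pain interferes with walking and sleep. The protocol takes a preoperative value for pain, opioid use, KOOS Jr and OKS, and gives no reason for leaving these two out.

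A baseline that was not collected cannot be supplied later. For KOOS Jr and OKS, an analysis plan can still choose to adjust for the preoperative score. For walking and sleep interference it can only borrow related measures. At stake are a description of change on two secondary outcomes, a direct check of whether the arms were alike on them at entry, and some precision.

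**Working it through.** **1. Which measures in question 3 have a preoperative value**

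| Measure | Preoperative | Postoperative |
|---|---|---|
| KOOS Jr | yes | weeks 2 and 6 |
| OKS | yes | week 6 (schedule also marks week 2) |
| NRS walking | no | to day 7 |
| NRS sleep | no | to day 7 |
| QoR-15 | no | day 1 |
| Length of stay | not possible | at discharge |

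Four of the six have no baseline, for different reasons. Length of stay cannot have one. QoR-15 is described as a measure of recovery after anaesthesia, so a day-1 level suits its purpose. The walking and sleep ratings are the two where a baseline is both meaningful and absent.

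**2. The plan's own figure.** The Power Calculation covers VAS-P only: 22 per arm, above 95% power, 20 mm, 5% level (taken as two-sided). The quoted SDs pool to √((16.8² + 15.0²)/2) = 15.93 mm at 48 hours and √((16.6² + 20.1²)/2) = 18.43 mm at 72 hours. By the noncentral t, power with 22 per arm is 98.3% and 94.0%, so the figure is broadly reproduced. It says nothing about walking or sleep, for which the protocol gives no effect size, SD or correlation.

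**3. Chance imbalance at entry.** With 23 per arm, the difference between two baseline means has standard error √(2/23) = 0.295 SD. By the normal approximation, an imbalance of at least 0.3 SD in either direction occurs in about 31% of such trials (0.3/0.295 = 1.02), and one of at least 0.5 SD in about 9% (0.5/0.295 = 1.70). This is ordinary sampling variation, already allowed for in the standard error of the unadjusted comparison.

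**4. Precision gained by adjustment.** Let r be the correlation between the preoperative and postoperative score. Adjusting by analysis of covariance multiplies the residual variance by 1 − r², so the effective size per arm is 23/(1 − r²) and a true difference of 0.7 SD acts like 0.7/√(1 − r²). Both r and the 0.7 SD are assumptions. Two-sided 5% power from the noncentral t:

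| r | 1 − r² | Effective n per arm | Power |
|---|---|---|---|
| 0 | 1.00 | 23.0 | 64.1% |
| 0.15 | 0.98 | 23.5 | 65.1% |
| 0.3 | 0.91 | 25.3 | 68.2% |
| 0.4 | 0.84 | 27.4 | 71.7% |
| 0.5 | 0.75 | 30.7 | 76.4% |
| 0.6 | 0.64 | 35.9 | 82.7% |

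The degree of freedom spent on the covariate lowers these powers by less than 0.1 percentage point.

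**5. Why not change scores.** A change score has variance 2(1 − r) relative to the postoperative score alone. At r = 0.3 this is 1.4, and it breaks even only at r = 0.5. Below r = 0.5, change scores would be less precise than having no baseline at all.

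**The case against.** The strongest reply is that the trial does not need a baseline to answer which arm does better. Allocation is 1:1 at random, so the difference in postoperative means is unbiased, and chance imbalance is part of the sampling error. That is right. A reader might infer that long-standing interference with walking or sleep is mixed into the treatment effect, or that question 3 cannot be answered for these items. The documents support neither inference.

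A second reply is that improvement is loosely used: length of stay stands in the same list, the secondary objectives speak of comparisons, and the analysis section compares group means. This also stands, and it is why QoR-15 and length of stay need only a change of wording.

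Third, a reader might infer that the planned comparisons lose precision. Against the plan as written they do not, because the t-test or Wilcoxon test uses no baseline even for KOOS Jr and OKS. The gain in the table needs both the new baseline and an adjusted analysis.

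Fourth, it would go too far to say that imbalance cannot be seen or handled at all. PDI, OKS, KOOS Jr and VAS-P are taken before surgery, preoperative scores are to be compared between arms, and an analysis plan could use them as covariates. These are related measures rather than the same items, so the check is partial, and the gain from the two new items beyond them would be smaller than the table shows.

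Finally, the preoperative window extends to 6 months before surgery. A 24-hour recall item asked that early could correlate only weakly with scores in the week after surgery. This bears on when to ask the item, not on whether to ask it.

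**Conclusion.** The point holds as a minor one. Question 3 speaks of improvement in walking and sleep interference, and the schedule does not allow within-patient improvement to be described for either. Imbalance at entry on these items can be examined or adjusted for only through related measures. The treatment comparison is not biased, the primary outcome is untouched, and no planned estimate becomes invalid.

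The size depends on a correlation that the documents do not give. For an assumed difference of 0.7 SD and 23 per arm, adjustment adds about 4 points of power at r = 0.3 and 12 at r = 0.5, and about 1 point at r = 0.15. The true gain would be less if the analysis already adjusted for the related baselines.

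**What to change.** Add the two 0-10 ratings, pain interference with walking and with sleep over the past 24 hours, to the pre-op column of the Patient Evaluation Schedule and to the preoperative list. Ask them at consent, which the Randomisation section places usually on the day before surgery, rather than at any time in the 6-month window, and complete them before the allocation envelope is opened.

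In Data Capture and Analysis, compare the postoperative walking and sleep scores with the matching preoperative score as covariate (analysis of covariance), not as change scores. Without this second step the new baseline adds no precision.

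Reword question 3 so that QoR-15 and length of stay are compared as postoperative levels, and keep improvement for measures that have a preoperative value.

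The cost is two single items in a questionnaire set that patients already complete, about a minute each patient, and one degree of freedom per analysis. If the items are not added, the rewording should cover walking and sleep as well; that costs nothing.

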The minimal clinically important difference is defined as the smallest change in a measurement that signifies an important improvement in a symptom. MCID for VAS-P in acute pain management has a wide range, ranging from 8-40 mm, with a median of 17 mm [29]. In a review across 570 randomised controlled trials on postoperative pain management after total hip and knee arthroplasty, the median MCID for VAS-P was found to be 15 mm at rest and 18 mm during movement [30]. Another study demonstrated the mean MCID for VAS postoperative pain improvement in TKA patients to be 22.6 mm [33]. There is yet to be a standardised value for postoperative VAS-P MCID, but based on recent literature and consensus we have chosen an MCID of 20 mm to suggest clinically relevant improvements in pain relief between the intervention and control groups [34].

Using this data, a priori power analysis was calculated using this data, which found that 22 patients in each arm would provide >95% statistical power to detect the expected difference in pain relief (MCID of 20 mm) at the 5% significance level between IORA Diclofenac and systemic (IV) Diclofenac. An additional patient in each group (5%) will bring each group to 23 patients to account for loss of follow up.

Inclusion Criteria

Informed consent obtained - both written and verbal

Patient undergoing primary total knee arthroplasty for Osteoarthritis

Age \geq 18 and \leq 80 years old (inclusive)

Exclusion Criteria

Patient lacking capacity to consent to the research project

BMI ≥ 40

Pregnancy or suspected pregnancy

Pain Catastrophising Scale score ≥ 30 points

Previous infection of knee joint

Rheumatoid/inflammatory arthritis

Undergoing bilateral total knee replacement, revision total knee arthroplasty, or any additional procedure outside of a primary total knee arthroplasty

Precluded from having general anaesthesia

Patients with lower limbs not amenable to effective tourniquet use

Contraindications to Diclofenac:

[figure not shown]
- Established allergy or hypersensitivity to Aspirin or other NSAID including attacks of asthma, angioedema, urticaria, or acute rhinitis
- Severe renal disease (GFR<30 mL/min/1.73m²)
- Severe cardiac failure
- Hepatic failure
- Active gastric or intestinal ulcer, bleeding or perforation
- Recent myocardial infarction (within last 12 months)
- History of asthma
- History of haemorrhagic diathesis

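### The >95% power is stated for an expected difference of 20 mm, but 20 mm is a chosen MCID and the cited trial showed 13.0 to 13.9 mm for a larger contrast

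*Protocol*

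**What the plan says.** All references are to the Protocol.

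- **Source of the calculation (Power Calculation).** "Sample size was calculated based on previously published data investigating the efficacy of perioperative Celecoxib (a NSAID) on postoperative pain (VAS pain) after TKA". That trial compared celecoxib plus PCA morphine with a group on PCA morphine alone. Mean VAS in the celecoxib arm is given as 21.3 ± 16.8 mm at 48 hours and 17.8 ± 16.6 mm at 72 hours. For the other arm, "VAS pain scores in the control group were 34.3 ± 15.0 at 48 hours, and 31.7 ± 20.1 at 72 hours".
- **Source of the 20 mm (Power Calculation).** After listing several published MCIDs the protocol says that "based on recent literature and consensus we have chosen an MCID of 20 mm to suggest clinically relevant improvements in pain relief". One of those listed comes from a review of hip and knee arthroplasty trials, where "the median MCID for VAS-P was found to be 15 mm at rest and 18 mm during movement".
- **The power statement (Power Calculation).** "22 patients in each arm would provide >95% statistical power to detect the expected difference in pain relief (MCID of 20 mm"). The test level is 5%. The statement is introduced as a calculation that used these data. No SD, time point or sidedness is given.
- **Use of 20 mm in interpretation.** The threshold returns under Postoperative Outcome Measurements: "MCID) of 20 mm for VAS-P scores will be used to determine the clinical significance of pain relief". Data Capture and Analysis repeats the rule and adds that it need not coincide with statistical significance.
- **The contrast under test.** The description of the study groups after the Exclusion Criteria gives both arms 75 mg of diclofenac, one by the intraosseous and one by the intravenous route. The standard postoperative regimen includes celecoxib for all patients.

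**The concern.** An MCID says how large a difference must be to matter. It does not forecast the difference a treatment will produce. The power sentence merges the two: it calls the MCID the expected difference and credits it to a trial whose observed differences were about two thirds as large. That trial also tested the presence of an NSAID against its absence, whereas here only the route of the same dose differs.

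Two consequences follow. A reader will take >95% as the chance of success if the treatment works as expected, which the cited data do not support. And if the result is not significant, the combination of >95% power and a 20 mm rule invites the conclusion that no worthwhile benefit exists, when benefits well below 20 mm may not have been excluded.

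**Working it through.** **Inputs.** n = 22 evaluable per arm, 1:1, 5% level, target 20 mm, and the source means and SDs, all from the protocol. Assumed because not stated: a two-sided test, a single time point, and the source trial's pooled SD.

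**Pooled SD** (equal weights)
- 48 h: √((16.8² + 15.0²)/2) = 15.93 mm
- 72 h: √((16.6² + 20.1²)/2) = 18.43 mm

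**Source differences**
- 48 h: 34.3 − 21.3 = 13.0 mm
- 72 h: 31.7 − 17.8 = 13.9 mm
- 20/13.0 = 1.54 and 20/13.9 = 1.44, so the target is about one and a half times the source's whole NSAID effect.

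**Power.** Two-sample t-test with noncentrality λ = δ / (s√(2/n)), 42 degrees of freedom, critical value 2.018. The standard error s√(2/22) is 4.80 mm (48 h SD) or 5.56 mm (72 h SD).

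| Difference δ | λ, SD 15.93 | Power | λ, SD 18.43 | Power |
|---|---|---|---|---|
| 20 mm (plan's target) | 4.17 | 98% | 3.60 | 94% |
| 15 mm | 3.12 | 86% | 2.70 | 75% |
| Source's own: 13.0 mm (48 h), 13.9 mm (72 h) | 2.71 | 75% | 2.50 | 69% |
| 10 mm | 2.08 | 53% | 1.80 | 42% |

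The first row reproduces the plan's figure: above 95% with the 48 h pooled SD and marginally below with the 72 h one (94.9% by the normal approximation). With the celecoxib-arm SDs alone, 16.8 and 16.6 mm, power for 20 mm is 97.1% and 97.4%. With the largest single SD, 20.1 mm, it is 89.7%.

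**Difference detectable with 80% power at 22 per arm:** 13.8 mm (SD 15.93) or 15.9 mm (SD 18.43).

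**One-week mean.** The Objectives section says means are calculated over one week. For seven daily scores with equal SD s and common within-patient correlation ρ, the SD of the mean is s√((1 + 6ρ)/7). At ρ = 0.7 the factor is √(5.2/7) = 0.862, giving 13.73 and 15.89 mm. Power is then 87% for 13.0 mm and 81% for 13.9 mm. At ρ = 0.5 it is 94% and 90%. The correlation is an assumption, since the protocol gives none, and the calculation also takes the effect to be the same on every day.

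**What a non-significant result would leave open.** At a single time point the 95% CI half-width is about 2.018 × 4.80 = 9.7 mm or 2.018 × 5.56 = 11.2 mm. An observed difference of 8 mm, for illustration, would not be significant, yet its interval would reach 8 + 9.7 = 17.7 mm or 8 + 11.2 = 19.2 mm.

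**The case against.** The strongest reply is that the protocol is open about what 20 mm is. The power sentence itself labels it the MCID, powering on an MCID is a standard target-difference approach, and the celecoxib trial may have been meant to supply variability only. The protocol also concedes that data on intraosseous administration for pain are scarce. All of this stands. What it does not rescue is the word *expected*, or the statement that the calculation used those data, when the only treatment effect they contain is 13.0 to 13.9 mm.

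A second reply is that single-time-point power understates power for a one-week mean. That also stands: at correlation 0.7 the 69 to 75% becomes 81 to 87%. A reader might infer that the trial is weak for any plausible benefit; the documents do not show that.

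Third, the plan separates clinical from statistical significance and provides 95% CIs. But the CIs are specified for VAS-P scores at each time interval, not for the difference between arms.

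Three further inferences are tempting and unsupported:

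- *That 20 mm is close to unattainable.* If the intravenous arm scored like the source's celecoxib arm, a 20 mm gain would need means of 21.3 − 20 = 1.3 mm at 48 h and 17.8 − 20 = −2.2 mm at 72 h. This rests on an assumed control mean and covers only 48 to 72 h. Pain is also scored from 1 to 24 h, for which no control means are given, and the rationale for higher local concentrations and a depot effect is not refuted by the cited data.
- *That >95% is true only with the 48 h SD.* It also holds with the 72 h celecoxib-arm SD (97.4%).
- *That 15 mm should replace 20 mm.* The protocol also cites 17, 18 and 22.6 mm and a range of 8 to 40 mm. Its Objectives mention evoked movement as well as rest, although Postoperative Outcome Measurements restricts scores to rest. The choice of 20 mm lies within the cited evidence.

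**Conclusion.** The point holds as a mislabelled power statement, not as an arithmetic error. The >95% is reproducible for 20 mm under reasonable SDs (98% or 94% with the pooled values). What fails is the claim that 20 mm is the expected difference and that the cited trial supports it. At that trial's own differences, 22 per arm gives 75% (48 h) or 69% (72 h), and 80% power is reached only at 13.8 or 15.9 mm.

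These figures assume a two-sided t-test, one time point, 22 evaluable patients per arm and the source's pooled SDs. Power for a one-week mean would be higher by an amount that depends on a correlation the protocol does not give. That the route effect should be no larger than the source effect is a judgement from the design (same drug and dose in both arms, celecoxib in both), not something the documents measure.

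**What to change.** No change in sample size is needed.

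1. **Power Calculation.** Replace the expected difference with the target difference (MCID). State the SD, time point and sidedness used. Report the range, for example: with 22 per arm, a two-sided 5% t-test at a single time point and SD 15.9 or 18.4 mm, power is 98% or 94% for 20 mm, 86% or 75% for 15 mm, and 75% or 69% for the 13.0 or 13.9 mm seen in the cited trial; 80% power is reached at 13.8 or 15.9 mm.
2. **Same paragraph.** Add that power for a one-week mean would be higher and depends on the assumed within-patient correlation, for example about 81 to 87% for 13 to 14 mm at correlation 0.7 over seven daily scores.
3. **Postoperative Outcome Measurements, and Data Capture and Analysis.** Keep 20 mm as the chosen MCID, but judge clinical relevance from the 95% CI of the between-group mean difference, so that a non-significant result is not read as excluding benefits smaller than 20 mm. The 15 mm at-rest median may be shown beside it as a sensitivity reference.

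The cost is rewording by protocol amendment, which needs ethics committee approval under the protocol's own rules, and a less flattering power statement.
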